needs and circumstances of midlife and older Latinos living with HIV. HOLA builds on prior research using health promotion to prevent depression and anxiety in older Latinos. In the present context, HOLA uses a lay community health worker (CHW) to lead a health promotion program in order to reduce cardiometabolic risk and improve psychosocial functioning and health-related quality of life in midlife and older Latinos living with HIV. Such an approach could appeal to midlife and older Latinos living with HIV as a nonstigmatizing and culturally acceptable intervention. HOLA addresses multiple concerns that are prevalent in this community (cardiometabolic risk, psychological distress). In addition, cultural values and beliefs were included in the formative and development phases of the intervention to ensure that the different socio-cultural influences that have a role in the health of Latinos were incorporated. Thus, HOLA is the optimal choice to address an urgent medical and public health issue, and one that is rapidly growing. The objectives of this pilot study are two-fold: (1) to evaluate the feasibility and acceptability of HOLA among HIV-infected Latinos aged 50 and older and (2) identify modifications needed in the design of a larger, ensuing hypothesis testing study. HOLA, which is informed by Behavioral Activation and Social Learning theory is a CHW-led, multicomponent, health promotion intervention consisting of: (1) a social and physical activation session; (2) a moderately intense group walk led by a CHW for 45 minutes, 3x/week for 16 weeks; (3) pleasant events scheduling. The proposed pilot study will recruit and enroll 18 community dwelling Latinos living with HIV aged 50+. Participants will be assessed at three time points (baseline, post intervention, and 3 months post intervention) on measures of cardiometabolic risk factors (waist circumference, dyslipidemia, hypertension, and glucose), psychosocial functioning, and health-related quality of life. Consistent with recommendations from biostatistical workgroups funded by NIH, this pilot study is not powered to test a hypothesis. Rather, this pilot study is a requisite initial step in exploring an innovative application of the HOLA health promotion intervention.

5) **Inclusion and Exclusion Criteria***

Inclusion Criteria:

The following conditions must be met for study eligibility:

- are Latino (self-identified);
- are age 50+;
- are male;

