- are HIV infected but are virologically suppressed (viral load <200 copies/mL);
- volunteer informed consent
- have medical clearance by a physician;
- expect to stay in Miami for the next 6 months; and

IRB Study Number: 20181032

Version 8, Date: 07/16/2021

- have documented risk of cardiometabolic disease.

Exclusion Criteria:

Individuals meeting any of the following criteria will not be eligible to participate in the study:

- have a diabetes diagnosis;
- at baseline meet criteria for current major depressive disorder or generalized anxiety disorder;
- meet criteria for current alcohol or other substance abuse disorders;
- have a lifetime history of bipolar disorder or other psychotic disorder;
- have a diagnosis of any neurodegenerative disorder or dementia (Parkinson's disease, Alzheimer's, vascular, frontotemporal dementia, etc.) or significant cognitive impairment as indicated by a Mini Mental Status Exam score <24;
- have contraindications to physical activity outlined in the American College of Sports Medicine standards; (g) have high suicide risk i.e., intent or plan to attempt suicide in the near future (a response of "yes" to questions 3, 4, and/or 5 on the Paykel Questionnaire);
- are unable to complete 10 m walk test;
- currently residing in a nursing or group home;
- have a terminal physical illness expected to result in the death within one year;

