This study will not include women in that the specific research questions are targeted toward males. This study will specifically target Latinos. Individuals from other ethnic backgrounds are excluded as the study intervention is specifically tailored to address and target the specific needs and preferences of older Latinos with risk of cardiometabolic disease. This study is specific to only Latino males and will only report data on Latino males; findings from the study are intended to only be generalizable to Latino males. Both Black and White Latino males will be included in the study. We are not powered to detect differences between racial groups of Latino men. Previous research indicates that the outcomes in this study along with engagement with the intervention suggests no differences between racial groups of Latino males; no significant differences have been found in any outcomes in HOLA pilot data. We will use respondent self-report or self-identification to collect data on ethnicity and race. Though this application talks of racial/ethnic disparities and refers to Latino as an ethnicity, we are aware of the limitations of this construct. We acknowledge that ethnicity is a social construct and that Latinos are not a homogeneous, monolithic group even though the U.S. Census definition classifies them into one uniform ethnicity. Also, many racial/ethnic differences that have been identified in previous research are in fact confounded by socioeconomic status (SES). However, even though SES is indeed a central determinant of health status and overlaps with the concept of race, SES does not account for all racial health disparities.

6) **Number of Subjects***

18 older Latinos age 50+ will be enrolled.

7) **Study-Wide Recruitment Methods***

Recruitment procedures will protect participant confidentiality.

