Project Evaluation: we will use a project evaluation questionnaire developed by investigators at the CNSA and used in previous studies. The items are a mix of rating scales, yes/no questions, and open-ended questions that allow participants to give feedback in short answer format with specific interest in understanding the participants' opinions regarding the specific components of the intervention.

After the baseline assessment, participants will be enrolled into the HOLA intervention.

Intervention Description: Content and Structure of HOLA

HOLA is a 16-week multi-component, health promotion intervention for older Latinos with subthreshold depression or anxiety. Aside from the maintenance phase (described below), the length and content of the intervention remain unchanged from the pilot study.

The first component of HOLA consists of two manualized social and physical activation sessions. Prior to beginning the group walk phase, each participant will meet individually with a CHW for the physical and social activation session. This session will last 30 minutes. The purpose of this session is to (a) educate potential participants about the goals of the intervention; (b) to motivate participants to engage in physical activity; (c) to increase participants' social activities (d) identify potential obstacles that may interfere with meeting the demands of the intervention; and (e) to brainstorm ways to overcome these obstacles. Participants will meet individually with the CHW for 30 minutes during week 8 to discuss progress of physical and social activity goals. These meetings will be held in the participants' homes.

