As a pilot study, we will evaluate the feasibility of recruitment, assessment procedures, retention, acceptability, and implementation of HOLA in a sample of midlife and older Latinos living with HIV (**Aim 1**). Consistent with recommendations from biostatistical workgroups funded by NIH, this pilot study is not powered to test a hypothesis. This approach to analysis of feasibility data mirrors the structure of the first HOLA trial and other pilot trials conducted at the CNSA. Successful recruitment will be defined as meeting 100% of targeted sample (N = 18), with 20% or less of eligible subjects refusing to participate. Adequate retention will be defined as 85% or more of randomized subjects completing the post-intervention assessment. Acceptability is defined as 80% or more of sessions attended by subjects. To identify modifications needed in the design of a larger, confirmatory randomized controlled trial (**Aim 2**), we will use a project evaluation questionnaire developed by investigators at the CNSA and used in previous studies. The items are a mix of rating scales, yes/no questions, and open-ended questions that allow participants to give feedback in short answer format with specific interest in understanding the participants' opinions regarding the specific components of the intervention. To explore changes in cardiometabolic risk factors (waist circumference, dyslipidemia, hypertension, and glucose), psychosocial functioning (depression and anxiety severity, social support), and health-related quality of life (**Aim 3**), a one-way ANOVA will be used to illustrate the change in scores from baseline to post-intervention in all the outcome measures used.

A repeated measures ANOVA, as we have proposed, is appropriate to explore the intervention effects on cardiometabolic risk factors,

IRB Study Number: 20181032

Version 8, Date: 07/16/2021

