Overall, study personnel and collecting outcomes data are all experienced in conducting clinical research and are able to engage subjects without causing them distress. If a subject finds the research procedures to be upsetting or aversive, they will have the option to withdraw from the study. Participation will be completely voluntary, and will not affect the treatment they are receiving at the UM/JMMC Adult HIV Outpatient Clinic. Participants will be told that they may choose not to answer any questions and may decide to terminate the interview at any time. Research staff will be instructed to terminate interview sessions if participants appear to be stressed by the process. Additionally, the research staff will know how to link participants immediately with treatment personnel including case managers or therapists if participants appear to be stressed.

Protection for Suicide and Depression Risk: Subjects who become suicidal or psychotic will be withdrawn from the study and offered (or when necessary, involuntarily given) appropriate treatment. Our screening process will include an assessment to identify participants at risk of suicide. Potential participants will be told before screening that a positive screen will lead to disclosure of this information to their primary care provider (PCP) or to a mental health professional to maintain safety. The Paykel Suicide Items 152 will be administered by a trained RA at every baseline and follow up assessment. In the unlikely event that suicidal ideation is detected the following steps will be taken. First, the RA will inform the participant that this information is very important and needs to be shared with his/her PCP or with a mental health professional immediately (as discussed prior to the screener). Second, the RA will then

IRB Study Number: 20181032
Version 8, Date: 07/16/2021

contact the principal investigator (PI) to discuss the situation. Third, the PI will contact the participant's PCP to ensure the participant is evaluated promptly for safety. Fourth, if the PCP is not available, the PI will arrange for transportation to the nearest emergency room. The RA will remain with the participant until the individual is assessed by a mental health professional or ER physician.

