If a participant meets criteria for major depressive disorder or an anxiety disorder, the following steps will be taken. First, the RA will seek written permission from the participant to contact his/her PCP or a mental health professional. Second, the RA will contact the PI to discuss the situation. Third, the PI will contact the PCP or a mental health professional informing them of their patient's positive screen. Fourth, the PI will coordinate with the PCP or mental health professional and the participant to set up an appointment.

Protection of Risk of Physical Discomfort: Because the HOLA intervention involves physical exercise, to which some participants may be unaccustomed, we will put several safeguards in place to avoid injury or harm. These safeguards have been used successfully in other studies involving exercise done by [name] (co-investigator). First, the 10 meter walk test will be used to evaluate walking ability. The use of this test is recommended in order to obtain the most valid clinical assessment of walking speed when using it as a 1-time indicator of health status. Second, all participants will be required to have a written medical clearance for participation in the study. In addition, all participants will be evaluated with a set of screening questions to identify individuals who may be at risk of harm from engaging in exercise. We will require these individuals to additionally obtain written recommendations for physical exertion from their physicians specifically responding to the identified health concern before engaging in HOLA. Third, CHWs will work with participants to set exercise goals that are safe and reasonable in relation to their exercise capacity. Furthermore, exercise plans and instructions to participants will be within the accepted range recommended by the American College of Sports Medicine guidelines. Fourth, CHWs will supervise all walks to observe participants' ability to tolerate exercise. CHWs will maintain a list of the phone numbers of the participants' physicians to contact with health concerns about participants. CHWs will be certified in CPR and will have cell phone capacity in the unusual event of a medical emergency. In the case of minor effects of exercise such as muscle soreness, CHWs will be trained to provide advice regarding stretching or other remedies to ameliorate symptoms. If symptoms worsen, the exercise protocol will be modified after discussion with [name].

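### Does a retention criterion based on randomized subjects leave a single-arm pilot without a usable denominator?

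*Combined protocol and SAP*

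**What the plan says.** Section 3 makes retention one component of Aim 1, the primary outcome, alongside recruitment, assessment procedures, acceptability and implementation. Section 10 gives its success rule: "Adequate retention will be defined as 85% or more of randomized subjects completing the post-intervention assessment". No other retention rule appears.

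The rest of the protocol describes a single group. Section 4: "The proposed pilot study will recruit and enroll 18 community dwelling Latinos living with HIV". Section 6: "18 older Latinos age 50+ will be enrolled". Section 8: "After the baseline assessment, participants will be enrolled into the HOLA intervention". No comparator, allocation ratio or randomization procedure is described for this study. In the aims, the randomized trial is the future confirmatory one of Aim 2.

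Section 10 also says of the feasibility analysis: "This approach to analysis of feasibility data mirrors the structure of the first HOLA trial". That may be where the word came from.

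**The concern.** A success rule for the primary aim names a population that does not exist here. Taken literally, the percentage is a count over zero and cannot be scored, so the analyst has to supply the denominator.

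The protocol also has steps at which groups of men might separate:

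- Section 5 excludes men who "at baseline meet criteria for current major depressive disorder or generalized anxiety disorder", so some could consent and never enter HOLA.
- Section 13 asks men flagged by the exercise screening questions for "written recommendations for physical exertion from their physicians specifically responding to the identified health concern before engaging in HOLA", so some might enter and never start.
- Section 13 also states: "Subjects who become suicidal or psychotic will be withdrawn from the study". The retention sentence does not say whether such men still count.

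With a target of 18, one man is 1/18 = 5.6 percentage points. If the denominator were chosen after the data were seen, a count restricted to starters or to remaining men could pass where the full count fails.

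**Working it through.** **Inputs.** Threshold 85% (section 10); target 18 (sections 4, 6 and 10); entry into HOLA after baseline (section 8). The protocol gives no retention count, so there is no figure of its own to reproduce.

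**Rule with the enrolled men as denominator.** The smallest passing count is 0.85 x n, rounded up. For n = 18, 0.85 x 18 = 15.3, so 16. Then 16/18 = 88.9% passes, 15/18 = 83.3% fails, and at most 2 men may miss the post-intervention assessment.

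**How far another denominator could move the verdict.** The protocol gives no counts for consented, started or remaining men. I assume gaps of 0 to 3 men from the 18 enrolled, and that men outside a smaller set do not complete. No probability is attached to any gap.

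| Denominator | n | 0.85 x n | Completers needed | Counts at which the verdict differs from k/18 |
|---|---|---|---|---|
| Enrolled | 18 | 15.30 | 16 | none |
| Starters or remaining, gap 1 | 17 | 14.45 | 15 | 15 (15/17 = 88.2%) |
| Gap 2 | 16 | 13.60 | 14 | 14, 15 (14/16 = 87.5%; 14/18 = 77.8%) |
| Gap 3 | 15 | 12.75 | 13 | 13, 14, 15 (13/15 = 86.7%; 13/18 = 72.2%) |
| Consented, gap 1 | 19 | 16.15 | 17 | 16 (16/19 = 84.2%) |
| Gap 2 | 20 | 17.00 | 17 | 16 (16/20 = 80.0%) |
| Gap 3 | 21 | 17.85 | 18 | 16, 17 (17/21 = 81.0%; 17/18 = 94.4%) |

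The arithmetic allows a difference. Whether it matters depends on whether the text supports any row but the first.

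**Consented men.** Section 5 makes men with the named baseline diagnoses ineligible, and section 8 places entry into HOLA after baseline. They are therefore not enrolled into the intervention, and nothing in the retention sentence reaches back to consent.

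**Starters only.** The extra physician recommendation is due before a man takes part in HOLA, and medical clearance is already an inclusion criterion in section 5. The text does not place this step after enrollment, so it need not produce any enrolled non-starters.

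**Remaining men only.** A man withdrawn after entry who misses the assessment is a retention failure. Removing him from the denominator would remove what the measure is meant to count.

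**What the word itself implies.** A denominator of randomized subjects is conventionally everyone allocated, whether or not they start or stay. In a single-arm study the matching point is entry into the intervention after baseline. That settles both open questions: non-starters and withdrawn men stay in.

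**How much rests on one man.** The exact 95% interval is 65.3% to 98.6% for 16/18 and 58.6% to 96.4% for 15/18. These overlap almost entirely, so the 85% line is a benchmark and not a sharp test.

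**The case for a change.** The strongest reply is that a primary-aim criterion should not need inference. The sentence is wrong on its face, no section equates randomized with enrolled, and the table shows that one man can turn a fail into a pass. Naming the population would take one phrase and rule out a choice made after the data are in.

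The wording error stands, and so does the arithmetic. The consequence does not. The rival denominators are assumptions with no support in the text, and at a gap of zero nothing changes. The protocol ties no progression or stopping decision to the 85% figure: section 10 says the pilot is not powered to test a hypothesis, and the continuation review in section 11 mentions feasibility without citing this threshold. With 18 men, a report that gives both counts lets any reader rescore the rule.

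Section 11 also uses randomization as a time point and refers to 3-month assessments. Part of that text describes the earlier HOLA pilot, and the visit meant may be the one that section 4 places 3 months after the intervention, which section 8 counts as month 7. This concerns adverse-event timing and has no bearing on retention.

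**Conclusion.** The concern does not hold as a reason to change the plan. The word is a clerical slip, probably carried over from an earlier HOLA trial. The surrounding text supplies the denominator: the men entered into HOLA after baseline, including those who do not start or who withdraw. If exactly 18 enroll, at least 16 must complete. If another number enrolls, the 85% governs; 17 enrolled, for example, would need 15. Correcting the word would be harmless but would alter no result.

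This rests on two assumptions: that the analyst applies the usual all-entered convention, and that the report shows numerator and denominator. If retention were instead reported over starters or remaining men only, the table shows that the verdict could differ at one to three completer counts for gaps of one to three men. That would be a departure from the plan as it is naturally read, and not a use of latitude that the plan gives.

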IRB Study Number: 20181032

Version 8, Date: 07/16/2021

Full Protocol Title: Preventing Cardiometabolic Disease in HIV-Infected Latino Men through a Culturally-Tailored Health Promotion Intervention

Protocol Number (eProst ID): 20181032

Protocol Version: 8

Protocol Version Date: 7/16/2021

PI Name: [name].

NCT number: NCT03839212

IRB Study Number: 20181032

Version 8, Date: 07/16/2021

1) **Protocol Title**

Preventing Cardiometabolic Disease in HIV-Infected Latino Men through a Culturally-Tailored Health Promotion Intervention

2) **IRB Review History***

This protocol has not been submitted for review by an external IRB.

3) **Objectives***

This study will address the following specific aims and test the following primary hypotheses:

Aim 1 (primary outcome): To evaluate the feasibility of recruitment, assessment procedures, retention, acceptability, and implementation of HOLA in a sample of midlife and older Latinos living with HIV.

Aim 2 (secondary outcome): To identify modifications needed in the design of a larger, confirmatory randomized controlled trial.

Aim 3 (secondary outcome): To explore changes in cardiometabolic risk factors (waist circumference, dyslipidemia, hypertension, and glucose), psychosocial functioning (depression and anxiety severity, social support), and health-related quality of life in a sample of midlife and older Latinos living with HIV enrolled in the HOLA health promotion intervention.

In addition, a career development and mentoring plan has been developed, comprised of expert mentorship, scholarly didactics and seminars, hands-on experience, as well as measurable productivity, including peer-reviewed manuscripts and an NIH grant application.

4) **Background***

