In addition, we will also collaborate with another study, the Clinic Registry Project (IRB#20160911), which serves as a consent to contact database, to contact eligible participants. They will provide us with contact information for participants in their study who have consented to be contacted by other studies. When contacting participants, the CHW will follow the phone script for calling UHealth consent to contact participants that has been tailored to this study.

8) **Procedures Involved***

Participants will be assessed at three time points (before starting the study, 4, and 7 months after the first interview) on measures of cardiometabolic risk factors (waist circumference, dyslipidemia, hypertension, and glucose), psychosocial functioning, and health-related quality of life.

All participants will read and sign an informed consent document and a HIPAA Research Authorization – Form B approved by the University of Miami Institutional Review Board (IRB). They will initially be provided with a verbal summary of the study and for those who appear to have problems reading the consent form it will be read aloud. Participant payments will be graduated. Participants will receive \$15 on the first visit, \$25 on the second visit, and \$35 on the third visit (total of honoraria = \$75).

Prior to starting the baseline assessments, blood draws will take place at the UM/JMMC Adult HIV Outpatient Clinic. Study staff will obtain initial HDL-C, LDL-C, triglycerides, insulin, and HbA1c levels via review of the electronic medical records. Trained and certified research assistants (RAs) who have at least a bachelor's degree will conduct all assessments in private offices at the UM/JMMC Adult Outpatient HIV Clinic, at a private interview room at the CTRS located on the 7th floor of the Don Soffer Clinical Research Center, or the participant's home. To ensure privacy in the home, we will conduct the interview in a private room with a door of the participant's choosing away from any common areas. In the event that there are other people in the house, the door can be closed to maintain privacy. In the event that an in-person interview is not feasible then the interview will be

IRB Study Number: 20181032

Version 8, Date: 07/16/2021

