The third component consists of scheduling pleasant events. During the cool down phase of each walking session, the CHW will ask each participant to identify a pleasant event that they intend to do with another person before the next meeting. The CHW will be trained to problem solve (e.g. brainstorming) if a member of the group cannot think of a pleasant event. Subsequent sessions will start with participants reporting on how effectively they implemented their pleasant event plan while the CHW and the group provide positive reinforcement and feedback. This component provides a means to generalize the intervention into the participants' every day lives. Mood ratings will be taken directly before and after each walk so participants can see, in real time, changes in their moods. These motivational tools stem from our qualitative study in which participants reported feeling motivated to engage in health promotion when they received positive reinforcement through clear indicators of progress. Participants will walk at a centrally located public park.

The final component is a maintenance phase consisting of one "booster" walking session twice a month for three months post intervention to reinforce the behavior change and maintain the effects of the intervention. We believe that we are more likely to detect sustained effect if maintenance is provided.

Should unavoidable circumstances arise and in-person meetings are not possible then the CHW will have regularly scheduled phone call with the participants to maintain motivation for increased physical activity and pleasant events.

Management of safety concerns

If a participant meets criteria for major depressive disorder or an anxiety disorder, the following steps will be taken. First, the RA will seek written permission from the participant to contact his/her PCP or a mental health professional. Second, the RA will contact the PI to discuss the situation. Third, the PI will contact the PCP or a mental health professional informing them of their patient's positive screen. Fourth, the PI will coordinate with the PCP or mental health professional and the participant to set up an appointment.

9) **Data and Specimen Banking***

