psychosocial functioning, and health-related quality of life given that this type of analysis is often used in studies that investigate either changes in mean scores over three or more time points. In the exploratory analyses, we will use age, SES, and years of education as covariates. In addition, a list of current medications will also be collected at baseline. Should the participants' medications be dose-adjusted, changed altogether, or if they are started on new medications such as statins, then we will adjust for them in them in the exploratory analysis as well. Covariates will be tested as moderators of treatment response.

Maintenance of Confidentiality:

Our staff is CITI certified and trained with maintenance of confidentiality. The information provided by study participants will be held as personal and confidential to the extent permitted by law. In addition to the safeguards included as part of the recruitment and screening process by assigning a patient a study ID to de-identify participants, all study participants will be given the contact information for the Principal Investigators to answer any questions that may arise. Participants will be informed that they may end their participation at any time without affecting access to any other services they may receive from the UM/JMMC Adult HIV Outpatient Clinic. All study procedures will be conducted according to good clinical practice and all other relevant regulatory guidelines.

All electronic data will be stripped of identifiers and stored in password-protected files on servers at the University of Miami Center on Aging. These data are password secured for minimal access to authorized personnel associated with the study. For each data file, a code number will be assigned, and the master list, linking code numbers with names, will be stored separately. At the conclusion of the project, the record linking the assigned research number and participant identity will be destroyed. Data will be entered into password secured databases by staff authorized by the principal investigator to do this, and they will abide by confidentiality regulations of the HSRO. No subject will be identified by any published report.

11) Provisions to Monitor the Data to Ensure the Safety of Subjects*

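### Aim 3 is assigned two inconsistent analyses, and the plan does not say which governs or whether the 7-month visit is analysed

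*Combined protocol and SAP*

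**What the plan says.** Section 3 (Objectives) sets the aim: "Aim 3 (secondary outcome): To explore changes in cardiometabolic risk factors", together with psychosocial functioning and quality of life. Section 8 (Procedures Involved) gives the schedule: "Participants will be assessed at three time points (before starting the study, 4, and 7 months after the first interview". Section 4 (Background) gives the same three visits in other terms: "Participants will be assessed at three time points (baseline, post intervention, and 3 months post intervention". There is no comparison group; section 8 says "After the baseline assessment, participants will be enrolled into the HOLA intervention".

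Section 10 (Data Management) then describes the Aim 3 analysis twice. The first statement is that "a one-way ANOVA will be used to illustrate the change in scores from baseline to post-intervention in all the outcome measures used". The second, immediately after it, is "A repeated measures ANOVA, as we have proposed, is appropriate to explore the intervention effects on cardiometabolic risk factors" (the sentence goes on to the psychosocial and quality-of-life outcomes). Its justification is that the method is often used for "changes in mean scores over three or more time points". Covariates are listed for the exploratory analyses, but section 10 does not say which of the two models they enter, and it gives no rule for a man who misses a visit.

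**The concern.** With one cohort, visit is the only factor, and it varies within person. The two statements differ in the method they name and in the visits they appear to cover. The second refers to a repeated measures proposal, but no other part of the document contains one, so the reference cannot settle which statement governs.

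Two analysts following the text could therefore report different standard errors, intervals and p-values, and different visits, for every Aim 3 outcome. The 7-month visit matters because section 8 adds three months of booster walks after the intervention, on the reasoning that "We believe that we are more likely to detect sustained effect if maintenance is provided". Of the scheduled assessments only the 7-month one can show a sustained effect, and the only sentence that names a time window for Aim 3 stops before it.

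**Working it through.** The plan gives no significance level, SD, within-person correlation or effect size for Aim 3, so it has no figure to reproduce. The check compares the two possible readings of the text and then sizes the difference under stated assumptions.

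**The two readings**

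- *Reading A:* the first statement is run as an ordinary one-way ANOVA on two visits. Each man's two scores are treated as coming from different people, and month 7 is unused.
- *Reading B:* a one-way within-subject (repeated measures) ANOVA was meant. The error term is then right, but one sentence covers two visits and the other rests on three or more.

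Degrees of freedom with 18 complete cases and no covariates show that these are different tests:

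- Between-groups, two visits: F(1, 34)
- Within-subject, two visits: F(1, 17)
- Within-subject, three visits: F(2, 34)

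**Size under reading A**

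From the documents: n = 18 (section 6). Assumed: complete data, equal variances at the two visits, two-sided 5%, correlation ρ of 0.3, 0.5, 0.7 or 0.8, and, for power, a change of 0.5 SD.

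- One-way SE of the change = √(2/18) = 0.333 SD, whatever ρ is.
- Paired SE = √(2(1−ρ)/18).
- Ratio of the two = 1/√(1−ρ).
- Half-width one-way = t(0.975, 34) × 0.333 = 2.032 × 0.333 = 0.68 SD.
- Half-width paired = t(0.975, 17) × paired SE, with t = 2.110.
- Paired power is from the noncentral t on 17 df, with standardised change 0.5/√(2(1−ρ)).
- One-way power and type I error are by simulation of correlated pairs analysed with the pooled variance on 34 df.

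| | ρ = 0.3 | ρ = 0.5 | ρ = 0.7 | ρ = 0.8 |
|---|---|---|---|---|
| Paired SE (SD) | 0.279 | 0.236 | 0.183 | 0.149 |
| SE ratio, one-way to paired | 1.20 | 1.41 | 1.83 | 2.24 |
| Half-width, paired (SD) | 0.59 | 0.50 | 0.39 | 0.31 |
| Half-width, one-way (SD) | 0.68 | 0.68 | 0.68 | 0.68 |
| Power, paired | 39.4% | 51.6% | 73.3% | 88.5% |
| Power, one-way | 28.0% | 24.9% | 20.7% | 17.7% |
| Type I error, one-way | 2.2% | 0.77% | 0.11% | 0.02% |

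Coverage of the nominal 95% one-way interval is 100% minus its type I error: 99.2%, 99.9% and 99.98% for ρ of 0.5, 0.7 and 0.8. The error is thus conservative: the intervals are too wide. The estimated mean change is the same in both analyses.

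**Missed visits**

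Section 10 sets retention at 85% at the post-intervention assessment: 0.85 × 18 = 15.3, so at least 16 men. Suppose, for illustration, 16 men at 4 months and 14 at 7 months, missing at random: 14 with all three visits, 2 with baseline and 4 months, 2 with baseline only. Generalised least-squares standard errors under compound symmetry were compared with those from the 14 completers alone. For ρ of 0.5, 0.7 and 0.8, completer-only standard errors are larger by a factor of 1.08 at 4 months, and by 1.03, 1.03 and 1.02 at 7 months.

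**The case against.** The strongest reply is that reading A is not what the authors meant. The sentences are adjacent, the second refers back to something already proposed, and there is no between-person grouping in the design. The one-way ANOVA is then most naturally one within-person factor, and the table above does not apply. The three-or-more wording also leans towards all three visits being used. The two sentences might even be complementary, one illustrating the change to post-intervention and the other exploring the whole course.

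Much of this stands. Reading B is plausible and may well be the intended one. But it repairs only the name of the method. The phrase about three or more time points is a general remark about how the technique is used, not a statement of which visits this study will analyse, and the one sentence that names a window ends at post-intervention.

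Two narrower points also stand. The correlations and effect size are assumptions, and at ρ = 0.3 the gap is much smaller. The missing-visit gain from a mixed model is modest: at 4 months most of the 8% comes simply from using 16 rather than 14 pairs (√(16/14) = 1.069), which a paired comparison of available men also recovers. A mixed model is therefore a preference and is not needed to resolve the conflict.

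**Conclusion.** The concern holds and should be fixed. The plan gives two statements of the Aim 3 analysis that do not agree on method name or visits, and nothing ranks them. Under the literal reading, the standard error of change is 1.41 to 2.24 times too large for assumed correlations of 0.5 to 0.8 (1.20 at 0.3), given complete data on 18 men and equal variances. Under the within-subject reading there is no such loss, but the role of the 7-month visit is still undefined.

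The consequences are bounded. Aim 3 is secondary and exploratory, the pilot is expressly not powered for hypothesis tests, the Aim 1 feasibility criteria do not depend on this, and any error under the literal reading is conservative. Lack of power does not excuse an undefined analysis, however, because estimates and intervals are what an exploratory aim delivers.

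**What to change.** In section 10, delete the one-way ANOVA sentence and state one within-subject analysis for each outcome, with visit (baseline, 4 months, 7 months) as a categorical effect. Report the changes from baseline to 4 months and to 7 months with 95% confidence intervals.

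The preferred form is a linear mixed model with a within-person covariance structure and small-sample degrees of freedom, fitted to all available visits so that a man who misses one is not dropped. A three-visit repeated measures ANOVA with a stated rule for missed visits would also resolve the conflict. Keep the plan's covariates (age, SES, years of education and medication changes) in the exploratory adjusted analyses.

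It would also help to report the number of men at each visit, the SD of change and the within-person correlation, which are useful for planning the larger trial. If the mixed model is used, note that it does not remove bias when dropout depends on unobserved outcomes.

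The cost is wording in one section. No new data, visits or participants are needed.
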